7.5.2. Definition of Serious Adverse Events

An SAE is an untoward medical occurrence or effect associated with the use of a study drug at any dose, regardless of whether it is considered to be related to the study drug, which results in one of the following:

- Death. This includes all deaths on treatment or within 30 days after last study drug administration, including deaths due to disease progression. Any death occurring later than 30 days following the last dose need not be reported as an SAE unless it is a result of an event that started within the period covered by the on-study definition. The reported AE should be the event that caused the death. In addition, any AE resulting in death that occurs subsequently to the AE reporting period and that the investigator assesses as possibly related to the study drug should also be reported as serious.
- A life-threatening condition. This refers to an event in which the subject was at risk of
 death at the time of the event. It does not include an event that, had it occurred in a
 more severe form, hypothetically might have caused death.
- Hospitalization or prolongation of existing hospitalization (excluding hospitalizations for administration of the study drug, procedures required by the study protocol, or treatment-related diagnostic procedures; other planned hospitalizations; or hospitalizations related only to progression of disease). Progression of disease resulting in transfer to ICU, mechanical ventilation, or other medically important event (at the discretion of the investigator) would be considered SAEs. Treatments in the emergency room for procedures such as hydration that do not require admitting the subject to the hospital and observational durations in the emergency room for less than 24 hours do not fall into this category.
- Persistent or significant disability or incapacity or substantial disruption of the ability to conduct normal life functions.
- Any other medically important event that the investigator or the sponsor judges to be serious or which is defined as serious by the regulatory agency in the local country. These are AEs that might not be immediately life-threatening or result in death or hospitalization but might jeopardize the subject or might require intervention to prevent one of the other outcomes listed above. Medical judgment should be exercised in deciding whether an AE is serious based on above definition. Examples of such events are intensive treatment in an emergency room or at home for allergic bronchospasm, blood dyscrasias or convulsions that do not result in hospitalization, or development of drug dependency or drug abuse.
- A pregnancy resulting in spontaneous abortion, stillbirth, neonatal death, or congenital anomaly (including that in an aborted fetus).

Note that any SAEs occurring at any time up to Day 60 should be reported to the sponsor if the investigator becomes aware of them.

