7.5. Adverse Events and Serious Adverse Events

7.5.1. Definition of Adverse Events

An adverse event (AE) is any untoward medical occurrence associated with the use of a drug in humans, whether or not it is considered related to the drug. An AE can therefore be any

^a To be analyzed at a central laboratory.

^b Direct and indirect bilirubin will be measured if part of the local laboratory usual assessment panel. In the case of Tbili >2xULN direct bilirubin must be assessed (Section 6.1.1).

unfavorable and unintended sign (including an abnormal laboratory finding), symptom, or disease in a study subject who is administered study drug in this study.

For this protocol, untoward medical occurrences that should be reported as AEs include the following:

- All AEs during the course of treatment with study drug administration
- All AEs resulting from medication misuse, abuse, withdrawal, or overdose, of study drug
- All AEs resulting from medication errors such as dispensing or administration error outside of what is described in the protocol
- · Apparently unrelated illnesses, including worsening of a preexisting illness
- Worsening of symptoms related to COVID-19
- Injury or accidents. Note that if a medical condition is known to have caused the injury or accident (a fall secondary to dizziness), the medical condition (dizziness) and the accident (fall) should be reported as 2 separate AEs. The outcome of the accident (hip fracture secondary to the fall) should be recorded in source documents.
- Abnormalities in physiological testing or physical examination findings that require clinical intervention or further investigation (beyond ordering a repeat [confirmatory] test)
- Laboratory abnormalities that require clinical intervention or further investigation (beyond ordering a repeat [confirmatory] test) unless they are associated with an already reported clinical event. Laboratory abnormalities associated with a clinical event should be captured in the source documents. Laboratory abnormalities not requiring clinical intervention or further investigation will be captured as part of overall laboratory monitoring and should not be reported as AEs.

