#### **4.9.2. Secondary Efficacy Analyses**

##### **4.9.2.1. Respiratory Functions**

###### **The proportion of subjects requiring invasive ventilation at any point during the study**

Number and the percentage of subjects requiring invasive ventilation during the study will be summarized by treatment groups. Cochran Mantel-Haenszel test will be used to compare the treatment difference.

A by-subject listing will also be provided for subjects requiring invasive ventilation.

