#### **4.10.1. Adverse Events**

All adverse events (AEs) will be coded using the MedDRA. The MedDRA version will be indicated in the footnote of relevant AE tables based on the current version used in the clinical data.

AEs will be analyzed in terms of treatment-emergent adverse events (TEAEs), which are defined as any AEs that occurring on or after the first study treatment through 30 days after the last dose, or any AEs occurring before the first study treatment but worsening during the treatment through 30 days after the last dose.

A treatment related TEAE is defined as TEAE that is suspected (possibly or probably related) by the investigator to be related to the study treatment. The severity/intensity of AEs will be graded 1 to 5 according to the National Cancer Institute (NCI) Common Terminology Criteria for Adverse Events (CTCAE) version 5.0. For AEs not described in CTCAE criteria, the intensity will be assessed by the investigator as mild (Grade 1), moderate (Grade 2), severe (Grade 3), life threatening (Grade 4), and fatal (Grade 5).

An overview of TEAE summary by treatment groups table will be provided with following information:

- The number of subjects with at least one TEAE
- The number of subjects with at least one treatment related TEAE
- The number of subjects with at least one Grade 3 or Grade 4 TEAE
- The number of subjects with a Grade 5 TEAE (Fatal)
- The number of subjects with at least one SAE

The number of subjects with at least one TEAE leading to treatment discontinuation.

All TEAEs will be summarized by MedDRA system organ class (SOC), and PT. If a subject experiences multiple AEs under the same SOC, the subject will be only counted once for the SOC with the greatest severity. Similarly, if a subject experiences multiple AEs under the same PT and SOC, the subject will be counted only once for the PT with the greatest severity.

The table will be sorted by the descending order of the frequency of SOC then by the descending order of the frequency of PT under SOC based on the PTC299 column.

In addition, the following summary tables will be provided:

- All TEAE by descending frequency of PT
- All TEAE by maximum severity under each SOC and PT
- SAE by SOC and PT
- Treatment related TEAE by SOC and PT
- TEAE leading to treatment discontinuation by SOC and PT

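### The all-cause TEAE, Grade 3-4, fatal and SAE rows mix COVID-19 progression with other harm, and no pre-specified row separates them

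*Protocol*

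**What the plan says.** Protocol 7.5.1 lists "Worsening of symptoms related to COVID-19" among the occurrences to report as adverse events. Protocol 7.5.2 makes the following an SAE, with a reference to investigator discretion: "Progression of disease resulting in transfer to ICU, mechanical ventilation, or other medically important event". On deaths it adds: "This includes all deaths on treatment or within 30 days after last study drug administration, including deaths due to disease progression". There is one partial exception. The hospitalization criterion leaves out "other planned hospitalizations; or hospitalizations related only to progression of disease".

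SAP 4.10.1 defines a TEAE to include "any AEs that occurring on or after the first study treatment through 30 days after the last dose", with no exclusion for COVID-19 events. Its overview table has rows for any TEAE, treatment-related TEAE, Grade 3 or 4 TEAE, fatal TEAE, "The number of subjects with at least one SAE", and TEAE leading to stopping treatment. SAEs and TEAEs are also tabulated by system organ class and preferred term, and by-subject listings are planned.

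Some of the same clinical events are also efficacy or outcome measures. SAP 4.9.2.1 analyses "The proportion of subjects requiring invasive ventilation at any point during the study" as a secondary endpoint, and SAP 4.10.2 reports deaths at Days 28 and 60.

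**The concern.** In a hospitalized COVID-19 population, progression may account for many of the serious and severe events. A row that counts each subject once for any SAE then measures two things together: how the disease went, and whatever else happened to the subject. A drug that works lowers the first part, and a toxic drug raises the second. The row shows only the net result.

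Non-hepatic harm is where this matters. The protocol describes PTC299 as acting on rapidly dividing cells and suppressing immune responses (Section 1), and it monitors lymphocytes and hemoglobin (Section 6.1.2). The only adverse events of special interest are hepatic. Harm spread thinly over several non-hepatic terms would be sought mainly in the overall SAE and Grade 3-4 rows, and those are the rows that are mixed.

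The preferred-term tables do not supply the missing count. A subject can appear under several terms, so the number of subjects with at least one SAE other than progression cannot be obtained by subtraction. The listings would allow it, but no list of progression terms is fixed, so a grouping made after unblinding would be post hoc.

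**Working it through.** **The plan's own figures.** The documents state no SAE rate, safety margin or safety power. The figures borrowed below do reproduce:
- Day 28 improvement with exponential medians of 11 and 8 days: 1 − 0.5^(28/11) = 0.829 and 1 − 0.5^(28/8) = 0.912.
- Power with 326 events and a hazard ratio of 1.38: Φ(ln 1.38 × √326 / 2 − 1.96) = Φ(0.948) = 0.83, which agrees with the stated power of more than 80%.

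**Inputs.**
- 190 subjects per arm (Protocol 4.1).
- Progression-SAE risk d on placebo: assumed 25%, with a range of 10% to 30%. Protocol Section 1 says 25% to 30% of hospitalized cases develop severe respiratory complications. This is a proxy, not a rate for this trial.
- Effect on progression: assumed risk ratio 1/1.38 = 0.725, with 0.85 and 1.0 as alternatives. The plan gives 1.38 for improvement, not for progression.
- Other-SAE risk t on placebo: assumed 5%.

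**Formula.** With d and t taken as independent, total SAE risk = 1 − (1 − d)(1 − t). The other-SAE rate on PTC299 that makes the totals equal is

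t₁ = 1 − (1 − d₀)(1 − t₀) / (1 − d₁).

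**Offset, main case.** d₀ = 25%, d₁ = 25% / 1.38 = 18.1%, t₀ = 5%.
- Placebo total = 1 − 0.75 × 0.95 = 28.8%.
- t₁ = 1 − 0.7125 / 0.8188 = 13.0%, a 2.6-fold rise that shows as no difference.
- A separate row would have about 78% power to show 5% versus 13.0% (two-sided 0.05, normal approximation).
- If other SAEs only double, to 10%, the PTC299 total is 1 − 0.8188 × 0.90 = 26.3%. That is below placebo, although other SAEs are 5 points higher.

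**Offset, other assumptions, with t₀ = 5%:**

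| Progression SAEs, placebo vs PTC299 | Other-SAE rate on PTC299 fully hidden |
|---|---|
| 10% vs 7.2% | 7.8% |
| 17.1% vs 8.8% (the plan's Day 28 non-improvement rates, as a proxy) | 13.6% |
| 25% vs 21.3% (risk ratio 0.85) | 9.5% |
| 30% vs 21.7% | 15.0% |

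**Dilution, no effect on progression.** d = 25% in both arms, t = 5% versus 10%.
- Totals: 28.8% versus 1 − 0.75 × 0.90 = 32.5%. The 5-point excess shrinks to 3.75 points.
- Separate row: null standard error √(0.075 × 0.925 × 2/190) = 0.0270; alternative √[(0.0475 + 0.09)/190] = 0.0269. Power = Φ[(0.05 − 1.96 × 0.0270)/0.0269] = about 46%.
- All-cause row: standard errors 0.0473 and 0.0473. Power = Φ[(0.0375 − 1.96 × 0.0473)/0.0473] = about 12%.

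Power serves here only as a measure of how visible a difference is. The plan specifies no test for safety.

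**The case against.** The case on the other side has several parts, and much of it stands.

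- **Not every safety display is affected.** A reader might infer that all the overall rows are mixed, and the documents do not support that. The treatment-related row is filtered by the causality judgment of blinded investigators. Hepatic events of special interest, liver categories and worst laboratory grades have their own tables (SAP 4.10.3 to 4.10.4.1). The discontinuation row is only partly affected, because disease progression and adverse event are separate reasons for stopping treatment (SAP 4.3). The causality filter is still a weak substitute for a separate row, since attribution is hard in very sick patients.
- **Safety is descriptive.** The protocol synopsis says so. No planned test is made invalid; the loss is in what the counts can show.
- **Counting ventilation as both efficacy and safety is not in itself an error.** All-cause SAEs and deaths are valid measures of net harm and should remain. Because ventilation and deaths are also reported on their own, a difference in those parts of progression would be visible. That would show that the SAE row might be offset, but not by how much.
- **The SAE definition is not the fault.** It governs reporting and already leaves out hospitalization related only to progression. The gap is in the tabulation.
- **Excluding terms presumes that they are disease.** If the drug worsened infection or lung injury, a row without respiratory terms would drop that harm. This is a real limit, and the reason such rows can only supplement the full tables.

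DSMB procedures are left to a Charter that is not among the documents, so whether the board sees such a split cannot be judged.

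**Conclusion.** The point holds in a limited form. The any-TEAE, Grade 3-4, fatal and SAE rows combine progression with other harm, and nothing pre-specified separates them. Under the main assumptions a rise in other SAEs from 5% to 13.0% would be invisible in the SAE row. Over placebo progression rates of 10% to 30% with a risk ratio of 0.725, the hidden rate runs from 7.8% to 15.0%. With no effect on progression, the cost is dilution.

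These sizes depend on assumed progression and other-SAE rates, on an assumed effect on progression, and on independence between the two kinds of event. At the low end little is hidden: even a separate row would have only about 20% power to show 5% versus 7.8%. If PTC299 worsened disease, the mixing would add to the apparent toxicity. A reader might infer that the plan will conceal toxicity or that PTC299 has some to conceal. The documents support neither. This is a worthwhile, inexpensive improvement to the safety tables, not a defect in the primary analysis.

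**What to change.** Keep all planned all-cause tables, including all-cause death, as the main safety display. In SAP 4.10.1 add:

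1. Supplementary overview rows for any TEAE, Grade 3-4 TEAE and SAE, and an SAE table by system organ class and preferred term, all excluding a named list of COVID-19 progression terms. Candidates to consider are COVID-19, COVID-19 pneumonia, acute respiratory distress syndrome, respiratory failure and hypoxia.
2. Fatal events split into progression and other cause, shown beside the all-cause count.
3. A statement that the list is fixed on blinded data before database lock, and that the supplementary rows are read only beside the full tables, because a listed respiratory term could be drug-related.

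Separately, reconcile two protocol passages. The closing note of 7.5.1 makes any hospitalization resulting from an adverse event an SAE, and worsening COVID-19 is an adverse event. Section 7.5.2 excludes hospitalization related only to progression.

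The cost is a short blinded review of terms, a paragraph in the SAP and one repeated set of tables. No data collection or reporting duty changes, apart from whatever the reconciliation of those two passages requires.

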7.5.3. Adverse Events of Special Interest

Events that may be indicative of hepatotoxicity (including the lower level MedDRA term of hepatotoxicity or drug-induced hepatotoxicity) are considered adverse events of special interest (AESIs) and will be reported on an expedited basis. These include:

- ALT increase Grade ≥3 (>5×ULN)
- AST increase Grade ≥3 (>5×ULN)
- Tbili increase >2×ULN
- ALP $\geq 2 \times ULN$

All instances meeting the above criteria should be reported within 24 hours to the PTC Therapeutics Pharmacovigilance Department on the SAE form. If the event is considered non-serious by the investigator then the SAE form and AE CRF page should be marked as non-serious. Medically significant liver events that are considered SAEs and consist of marked elevations of LFTs and / or pre-specified AEs may also be included in expedited reporting.

7.5.4. Unexpected Adverse Events

The Investigator's Brochure contains the Reference Safety Information (RSI) which will be used for assessing expectedness. If an event is not listed in the RSI, it should be considered unexpected or if the AE occurs at a greater severity, specificity or frequency, it should be considered unexpected.

Any hepatic abnormalities/ hepatotoxicity (hyperbilirubinemia, aspartate aminotransferase increase, alanine aminotransferase increase) of Grade ≥4 will be considered unexpected.

7.5.5. Eliciting Adverse Event Information

The investigator is to report all directly observed AEs and all AEs spontaneously reported by the study subject/parent(s)/legal guardian/legally acceptable representative. In addition, each study subject/parent(s)/legal guardian/legally acceptable representative will be questioned about AEs at each scheduled clinic visit after study drug administration or during any telephone contact with the subject/parent(s)/legal guardian/legally acceptable representative. The type of question asked should be open-ended, for example, "How have you been feeling?" or a similar type of query.

7.5.6. Recording Non-serious AEs and SAEs

All AEs (both serious and non-serious) that occur in subjects during the AE reporting period must be recorded, whether or not the event is considered drug related. In addition, any known untoward event that occurs subsequently to the AE reporting period that the investigator assesses as possibly related to the investigational drug/product should also be recorded as an AE.

All AEs are to be recorded in the source documents and on the eCRF using concise medical terminology; whenever possible, terms contained in the Medical Dictionary for Regulatory Activities (MedDRA) should be employed. In addition, the following information should be recorded:

- Indication of whether the event is serious or non-serious (see Section 7.5.2)
- Relationship to study drug (see Section 7.5.7)

- Severity of the event (see Section 7.5.8)
- Onset date
- Resolution date, or date of death
- Action taken
- Outcome of the event

Classification of the event as serious or non-serious determines the reporting procedures to be followed.

7.5.7. Describing Adverse Event Relationship to Study Drug

The investigator should provide an assessment of the relationship of the AE to the study drug, ie, whether there is a reasonable possibility that the study drug caused the AE, using the considerations outlined in Table 5.

Table 5: Relationship of Study Drug to Adverse Event Relationship

	Description
Probable	A clinical event in which a relationship to the study drug seems probable because of such factors as consistency with known effects of the drug; a clear temporal association with the use of the drug; improvement upon withdrawal of the drug; recurrence upon re-challenge with the drug; lack of alternative explanations for the event.
Possible	A clinical event occurring coincident with administration of the study drug and which may or may not be explained by concurrent disease or other drugs or chemicals. Information on drug withdrawal or re-challenge may be lacking.
Unlikely	A clinical event with a temporal relationship to the study drug exposure that does not preclude causality but for which there is a clear alternate cause that is more likely to have caused the adverse event than study drug. Such alternatives include a concomitantly administered drug, the subject's disease state, other medical conditions, or environmental factors.
Unrelated	A clinical event, for which a relationship to the study drug seems improbable because of factors such as inconsistency with known effects of the study drug, lack of a temporal association with study drug administration, lack of association of the event with study drug withdrawal or re-challenge, and/or presence of alternative explanations for the event. Alternative explanations might include a known relationship of the adverse event to a concomitant drug, medical history of a similar event, the subject's disease state, other medical conditions, or environmental factors.

7.5.8. Grading of Severity of Adverse Event

The severity of AE will be graded using the Common Terminology Criteria for Adverse Events (CTCAE) Version 5.0 (refer to the study manual). For each episode, the highest severity grade attained should be reported.

If a CTCAE criterion does not exist, the investigator should use the grade or adjectives: Grade 1 (mild), Grade 2 (moderate), Grade 3 (severe), Grade 4 (life-threatening), or Grade 5 (fatal) to describe the maximum intensity of the AE. For purposes of consistency with the CTCAE, these intensity grades are defined in Table 6.

Table 6: Grading of Adverse Event Severity Grade

	Adjective	Description
Grade 1	Mild	Sign or symptom is present, but it is easily tolerated, is not expected to have a clinically significant effect on the subject's overall health and well-being, does not interfere with the subject's usual function, and is not likely to require medical attention
Grade 2	Moderate	Sign or symptom causes interference with usual activity or affects clinical status, and may require medical intervention
Grade 3	Severe	Sign or symptom is incapacitating or significantly affects clinical status and likely requires medical intervention and/or close follow-up
Grade 4	Life-threatening	Sign or symptom results in a potential threat to life
Grade 5	Fatal	Sign or symptom results in death

7.5.9. Adverse Event Reporting

Investigator site reporting requirements for AEs are summarized in Table 7.

Table 7: Investigator Site Requirements for Reporting Adverse Events

Event	Recorded on the eCRF	Reported on the SAE Report Form to PTC Pharmacovigilance Within 24 Hours of Awareness
Serious AE	All	All
Non-Serious AE	All	None
Exposure to the study	All (regardless of whether	Exposure during pregnancy, exposure
drug during pregnancy or	associated with an AE), except	via breastfeeding, occupational exposure
breastfeeding, and	occupational exposure	(regardless of whether associated with
occupational exposure		an AE)

Abbreviations: AE, adverse event; eCRF, electronic case report form; SAE, serious adverse event

All AEs should be followed up by the investigator until they are resolved, or the investigator assesses them as chronic or stable. The investigator should consider protocol guidelines and use his/her discretion in ordering additional tests as necessary to monitor the resolution of such events. In the event of additional investigations, the PTC Therapeutics Pharmacovigilance Department or designee should be informed via e-mail or fax. A subject withdrawn from the study because of an AE must be followed by the investigator until clinical recovery is complete and laboratory results have returned to normal, or until progression has been stabilized. Follow-up may need to continue after the subject has discontinued from the study, and additional investigations may be requested by the medical monitoring team.

The first day of AE reporting will coincide with the date of signing of Informed Consent.

